Supervision stage	V _S	V ₁	V ₂	V ₃	V ₄	
Supervision time	-1day	0	4weeks ±3	8weeks ±3	12weeks±3	
Informed consent	*					
Main evaluation indicators (MDS-UPDRS)	*		*	*	*	when necessary
Secondary evaluation indicators (NMSS、PDQ-39、10M-WT、H&Y、LDE)	*		*	*	*	when necessary
Demographic information^A	*					
Medical history^B	*					
Vital signs^C	*		*	*	*	*
Physical examination^D	*		*	*	*	*

Laboratory tests (hematology/biochemistry/urinalysis)^E	*		*	*	*	必要时
Blood biomarkers^F	*				*	
Film degree exam^G	*				*	
Previous/concomitant medications^H	*					
Adverse event	*	*	*	*	*	*

Remark:

A. Demographics will include the subject's date of birth, gender, ethnicity, education, marriage, occupational information;

B. Medical history includes comorbid diseases and other clinically significant past medical history, medication history, and surgical trauma history;

C. Vital signs will include blood pressure, pulse rate, respiration and temperature;

D. Physical examination includes medical physical examination and neurology specialist physical examination;

E. Clinical laboratory examination: blood routine, serum biochemistry, coagulation, ceruloplasmin, gene expression level;

F. Blood biomarkers: IL-2, APEO, α -synuclein, DJ-1 protein, etc.;

G. Imaging examination: MRA, SWI;

H. The type, dose, and time of previously used drugs.

1. Research background

Parkinson's disease (PD) is a relatively common degenerative disease of the central nervous system, and China's population has grown significantly over the past few decades, resulting in a rapid increase in the number of elderly people; 2016 Global Burden of Disease Study Report It is said that the number of PD patients in China accounts for about 23% of the total PD population in the world^[1]; by the end of 2020, it is estimated that the number of people with Parkinson's in China will be about 3.62 million, and it is estimated that by 2030, 50% of PD patients in the world will be Chinese^[2]. Parkinson's disease is mainly manifested by motor symptoms such as bradykinesia, rigidity, and tremor, as well as non-motor symptoms such as autonomic dysfunction, sleep disturbance, and hyposmia^[1].

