6.4 Exit criteria

- (1) Subjects should withdraw from the trial when they have abnormal vital organ function, allergic reactions to drugs, poor compliance, exacerbation of the disease, or serious adverse reactions that need to stop the treatment of the trial drug or use other treatment methods;
- (2) Subjects who are ineffective, cannot tolerate adverse reactions, wish to take other treatment methods, or request to withdraw from the trial without any reason.

7. Research Interventions

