9.1 Withdrawal Criteria

Reasons for a subject to withdraw from the study may include:

Subjects should withdraw from the trial when they have abnormal vital organ function, allergic reactions to drugs, poor compliance, exacerbation of disease or serious adverse reactions that require stopping the treatment of the trial drug or using other treatment methods;

Subjects who are ineffective, cannot tolerate adverse reactions, wish to take other treatment methods, or request to withdraw from the trial without any reason.

Subject withdrew informed consent and refused further follow-up;

Subjects lost to follow-up;

Subject died.

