9.3 Steps to withdraw from the study or discontinue study treatment

Subjects must be checked for efficacy and safety in accordance with the protocol for withdrawal from the study and final observation and follow-up, and AEs and outcomes must be fully recorded. The researcher can suggest or provide alternative treatment methods to the subjects according to the actual situation of the subjects.

If the subject refuses to come to the research center for further visits, their survival status should continue to be tracked unless the subject withdraws informed consent. In this case, no further study evaluations should be conducted and no further data should be collected.

10. Evaluation indicators

10.1 Primary endpoint: Modified MDS-UPDRS scale score (the revised version of the Movement Disorders Association Unified Parkinson's Disease Rating Scale, which has four main parts, including both physician and patient aspects, the first part is psychological, behavioral and emotional; the second Part is activities of daily living; the third part is motor symptoms; the fourth part is complications), SGB is carried out in three cycles, each cycle is carried out for 6-10 days, and the interval between each cycle is 20 ± 7 days; The first, second, and third cycles of Day0, Day5, and the last day were measured and recorded.

10.2 Secondary endpoints : NMSS (Non-motor Symptom Evaluation Scale), PDQ-39 (Self-rating scale for clinical evaluation of the quality of life in patients with Kinson's disease), H&Y classification (Classification of Parkinson's disease), LDE (levodopa equivalent dose), 10M-WT (10m walk test), cerebrospinal fluid and blood biomarkers, SGB were carried out for a total of three cycles, each cycle was carried out for 6-10 days, and the interval between each cycle was 20 ± 7 days; On Day0, Day5, and the last day of the third cycle, the scale data were measured and recorded. The researchers performed head MRI + susceptibility-weighted imaging on Day 0 of the first cycle and Day 10 of the third cycle, respectively, to compare the changes in the "swallowtail sign" of two successive head MRIs.

11. Adverse events, serious adverse events, adverse reactions

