13.1 Statistical Analysis Data Set Definition

① Intentional analysis set (Intention-to-treat population)

All subjects who participated in randomization were included.

② Full analysis set (Full Analysis Set)

According to the principle of intention-to-treat analysis (ITT), all subjects who were randomized and who had received at least one post-treatment efficacy assessment were included.

③ Compliant with the scheme set (Per-protocol Set)

All patients who met the trial protocol, had good compliance (80%-120% of medication), did not use prohibited medication during the trial or completed the contents of the case report form.

④ Security Analysis Set (Safety Analysis Set)

All enrolled cases, all patients who have used the trial drug at least once and have safety records after drug use, belong to the safety analysis set. This dataset is used for safety analysis.

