13.2.3 Missing data imputation

If the patient fails to complete the corresponding scale or CRF due to force majeure factors, it should be completed within one week of missing data; if the patient withdraws from the study or terminates the study treatment, the corresponding missing data need not be completed.

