13.2.6 Effectiveness Analysis

① **Primary endpoint:** Modified MDS-UPDRS scale score

Measurement data were expressed as mean \pm standard deviation ($\bar{x} \pm s$). For those with normal distribution and homogeneous variance, paired-samples t-test was used for intra-group comparison, two independent samples t-test was used for inter-group comparison, and t' was used for unequal variances. test. $P < 0.05$ was considered to be statistically significant.

② **Secondary endpoints:** NMSS scale, PDQ-39 scale, H&Y grade, LDE, 10M-WT, cerebrospinal fluid blood biomarkers, MRI+SWI changes

Measurement data were expressed as mean \pm standard deviation ($x \pm s$). For those with normal distribution and homogeneous variance, paired-samples t-test was used for intra-group comparison, two independent samples t-test was used for inter-group comparison, and t' was used for unequal variances. For skewed data, median + interquartile range ($m \pm Q$) was used, and nonparametric test was used; $P < 0.05$ was considered statistically significant.

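### Nothing requires the remaining MDS-UPDRS scores once a patient stops study treatment, and patients leave this open-label trial for outcome-related reasons, so primary scores can be lost selectively

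*Protocol*

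**What the plan says.** Section 13.2.3 first lets a form that was missed through force majeure be made up within a week. It then adds that "if the patient withdraws from the study or terminates the study treatment, the corresponding missing data need not be completed". This joins two events that the protocol elsewhere lists apart: withdrawal (9.1) and discontinuing study treatment (9.2).

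Section 6.4 removes patients from the trial on two lists of grounds. The first opens "Subjects should withdraw from the trial when they have abnormal vital organ function" and goes on to drug allergy, poor compliance, worsening disease and serious adverse reactions. The second covers "Subjects who are ineffective, cannot tolerate adverse reactions, wish to take other treatment methods" and those who ask to leave. Section 9.1 repeats both lists under the words "Reasons for a subject to withdraw from the study may include" and adds consent withdrawal, loss to follow-up and death. The last sentence of 11.5(2) adds another route: the trial process ends for a patient who no longer meets the entry criteria after a laboratory abnormality.

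On what happens next, 9.3 says "Subjects must be checked for efficacy and safety in accordance with the protocol for withdrawal from the study and final observation" and names no remaining visit. In the Visit Schedule, the row that begins "Main evaluation indicators (MDS-UPDRS" is marked at V2, V3 and V4 but is only conditional in the exit column. Vital signs and physical examination are required there.

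Section 4.2 makes the trial open to patients and investigators. Section 13.1 defines an intention-to-treat set: "All subjects who participated in randomization were included". For the primary endpoint, 13.2.6 states that "two independent samples t-test was used for inter-group comparison".

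**The concern.** Exacerbation and lack of effect are close to the primary outcome itself. Whether they apply is judged by people who know the arm. If such patients stop being scored, the groups compared at V2-V4 are no longer the groups that were randomised. The stated two-sample t-test can use only patients who have a score.

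Stopping blocks can happen only in the SGB arm, and would tend to favour SGB if poor responders stop. Exit for exacerbation or lack of effect can happen in either arm, and among controls it would work against SGB.

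This is a matter of trial conduct. A statistical analysis plan can choose how to handle missing scores, but it cannot recover scores that were never taken. Section 14.3 aims to hold dropout within 20%, while these rules allow loss that could be avoided.

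**Working it through.** **1. What is required after treatment stops**

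| Place | What it secures |
|---|---|
| 13.2.3 | Nothing; excuses the missing data |
| 6.4, 9.1, 11.5(2) | Nothing; end trial participation |
| 9.3 | An efficacy and safety check with a final observation; no named visit |
| Visit Schedule, exit column | MDS-UPDRS only if needed |
| 8.3 | V2 (4 weeks), V3 (8 weeks), V4 (12 weeks) as part of the treatment stage; silent on patients who have stopped |

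Section 7.2 gives 10 daily blocks per cycle and 20 days between cycles, so the cycles fall on days 1-10, 31-40 and 61-70. A patient who stops at V2 (day 28, 10 of 30 blocks given) has no secured V3 or V4. One who stops at V3 (day 56, 20 of 30) has no secured V4. In both cases the later monthly part III scores named in the synopsis are also unsecured.

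**2. The plan's own sample size (4.3)**

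n = (1.96 + 0.84)² × 2 × 9.58² / 10² = 14.4, rounded up to 15. Then 15 / 0.8 = 18.75, rounded up to 19 per arm. The stated figure reproduces. It allows for 19 − 15 = 4 losses per arm. That allowance protects power, not comparability.

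**3. Shift in the estimate (assumed losses)**

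The documents give no exit rates. Assume m = 1 to 4 of 19 SGB patients are lost, each g points short of the gain in the others. The difference is then overstated by g × m / 19:

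- g = 10 (no gain): 10/19 = 0.5 up to 40/19 = 2.1 points.
- g = 5 (half the gain): 5/19 = 0.3 up to 20/19 = 1.1 points.

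Lost controls who are g points worse than the other controls give the same size with the opposite sign.

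**4. False positives (assumed losses)**

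Simulation with no true effect, normal outcomes, SD 9.58, 19 per arm and a two-sided t-test at 0.05. The table gives the chance of a significant result favouring SGB.

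| Who is lost | m = 1 | 2 | 3 | 4 |
|---|---|---|---|---|
| SGB arm, at random | 2.5% | 2.5% | 2.5% | 2.5% |
| SGB arm only, from the worse 9 of 19 | 3.2% | 4.4% | 5.9% | 8.3% |
| SGB arm only, the very worst m | 5.6% | 9.4% | 14.3% | 19.8% |
| Very worst m in both arms | 3.4% | 4.2% | 4.4% | 5.1% |
| Very worst m of controls, SGB at random | 1.4% | 0.8% | 0.6% | 0.3% |

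The first three rows use 100,000 runs and the last two 20,000. Equal loss from the worse half of both arms gives 2.0% to 2.5% for every m, so no inflation. Equal loss of the very worst shifts the mean difference by about 0. Its modest excess is the same in both directions, because cutting the tail shrinks the estimated SD.

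**The case against.** Section 13.2.3 can be read mildly. Its first clause is about making up a missed form, and the second may say only that no make-up is needed. A reader might infer that it orders visits to end, but the text does not say so. Section 9.3 helps too: its heading covers discontinuing treatment, its efficacy check is mandatory, and it treats refusal of further visits as a special case, which suggests that others go on being seen. This softens the point but does not remove it. An exit check is not a score at the scheduled time, no sentence requires V2-V4 after treatment stops, and 6.4 and 9.1 end participation in the trial, not just the blocks.

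The first list in 6.4 ends with a condition about needing to stop the trial drug or use other treatment. That condition may limit the whole list. Some of the second list is the patient's own choice, and such patients may refuse visits under any wording. Both remarks lower the likely frequency. They also show that needing to stop the drug is what leads to exit from the trial.

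A reader might infer a contradiction with the all-randomised set in 13.1. The documents do not support that. Section 13.1 defines four sets and assigns none to the primary test, and that choice may stand in an analysis plan that is not shown.

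A reader might also count the Day 0, Day 5 and last-day scores of 10.1 as lost. They are tied to block cycles that a patient who has stopped no longer has. Nor does a stop at V4 (day 84) matter for the blocks, since all 30 are nominally given by day 70.

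**Conclusion.** The point stands as a gap in the collection rules that should be closed. Following the protocol as written, MDS-UPDRS scores at V2-V4 can go uncollected for reasons related to the outcome, in a trial where the arm is known.

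The frequency and net direction of any bias are unknown. A reader might infer that the trial is biased towards SGB, or that its false-positive rate is near 20%. The documents do not support either. The higher rates need loss of poor responders mainly from the SGB arm, while the exit grounds apply to both arms. Under the assumed one-arm loss of 1 to 4 of 19 from the worse half, 2.5% becomes about 3%-8%. Under equal loss from the worse half of both arms, or loss unrelated to outcome, it does not rise.

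These figures rest on the protocol's SD of 9.58, normal outcomes and assumed loss patterns. The gap in the text does not depend on them. The sample size of 19 per arm is not in question.

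**What to change.** 1. In 13.2.3 (replacing the second clause) and in 9.3, state: patients in either arm who pause or stop study treatment complete all remaining V2-V4 MDS-UPDRS and secondary assessments and the monthly MDS-UPDRS III scores unless they withdraw consent, and these scores enter the between-group comparison.
2. In 6.4, 9.1 and the last sentence of 11.5(2), make organ dysfunction, allergy, poor compliance, exacerbation, adverse reactions, lack of effect, use of other treatment and unresolved laboratory abnormality grounds for stopping study treatment only, not follow-up. Consent withdrawal, loss to follow-up and death remain exits.
3. In the exit column of the Visit Schedule, require an MDS-UPDRS score.

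The investigator's authority to stop treatment (9.2, 11.5) and the serious adverse event rule (11.6) are unchanged.

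This is a cheap improvement: wording in five sections and one table cell, with no added patients or procedures. The cost is keeping planned visits for the few who stop. The estimate may also be smaller because it includes them. If 4 of 19 SGB patients have no gain, it is 10 − 40/19 = 7.9 points, and t-test power with 19 per arm is about 70%. That compares with 79% for 15 per arm at 10 points. If those who stop do as well as the others, power with 19 per arm is 88%.

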13.2.4 Descriptive analysis

Measurement data were expressed as mean \pm standard deviation ($\bar{x} \pm s$). For those with normal distribution and homogeneous variance, paired-samples t-test was used for intra-group comparison, two independent samples t-test was used for inter-group comparison, and t' was used for unequal variances. test. The enumeration data were expressed as percentage (%), and the total effective rate between groups was compared by chi-square test. $P < 0.05$ was considered to be statistically significant.

13.2.5 Analysis of Baseline Data

Descriptive analysis of baseline data (including demographic indicators, etc.).

13.2.6 Effectiveness Analysis

① **Primary endpoint:** Modified MDS-UPDRS scale score

Measurement data were expressed as mean \pm standard deviation ($\bar{x} \pm s$). For those with normal distribution and homogeneous variance, paired-samples t-test was used for intra-group comparison, two independent samples t-test was used for inter-group comparison, and t' was used for unequal variances. test. $P < 0.05$ was considered to be statistically significant.

② **Secondary endpoints:** NMSS scale, PDQ-39 scale, H&Y grade, LDE, 10M-WT, cerebrospinal fluid blood biomarkers, MRI+SWI changes

Measurement data were expressed as mean \pm standard deviation ($x \pm s$). For those with normal distribution and homogeneous variance, paired-samples t-test was used for intra-group comparison, two independent samples t-test was used for inter-group comparison, and t' was used for unequal variances. For skewed data, median + interquartile range ($m \pm Q$) was used, and nonparametric test was used; $P < 0.05$ was considered statistically significant.

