	
 1. Those who are allergic to local anesthetics; 2. Those who are unable to cooperate with sports or non-motor function monitoring; 3. Exclude patients with Parkinson's superimposed syndromes, such as corticobasal degeneration, dementia with Lewy bodies, multiple system atrophy, progressive supranuclear palsy; and secondary Parkinson's syndromes, such as vascular parkinsonism, drug poisons or patients with Parkinson's syndrome caused by trauma; 4. Refuse to sign the consent form.

Key Interventions
	
Experimental group: standard treatment of Parkinson's disease + SGB
 
Control group: standard treatment for Parkinson's disease

Follow-up
	
Intervention follow-up period: On Day0, Day5 and Day10 of the first, second and third cycles, the visiting schedule was used to record the required information. The interval of each cycle was 1 month, and the total follow-up time was 3 months.
 
Follow-up period: Modified MDS-UPDRS (Revised Movement Disorders Association Unified Parkinson's Disease Rating Scale) III scores were collected every month after treatment.

Evaluation index
	
Primary end point: MDS-UPDRS score.
 
Secondary end points: NMSS (Parkinson's disease Non-motor Symptom Evaluation Scale), PDQ-39 (39-item Parkinson's disease questionnaire), 10M-WT (walking speed test), H&Y grading (Hoehn Yahr (modified) Parkinson's disease grading), LDE (dopa equivalent dose).

Statistical method
	
SPSS25.0 software was used to analyze the data, and the measurement data were expressed by mean and standard deviation ($\bar{X} \pm S$). For those with normal distribution and homogeneity of variance, paired sample T test was used for intra-group comparison, two independent samples T test was used for inter-group comparison, and t 'test was used for those with uneven variance. The count data were expressed as percentage (%), and the chi-square test was used to compare the total effective rate between groups. $P < 0.05$ was considered as statistically significant difference.

Study time
	
Expected enrollment time of the first subject: 2022-01-01
 
Expected enrollment time of the last subject: 2022-06-30
 
Expected end time: 2024-06-30

Visit Schedule

	Screening stage	Intervention follow-up period			Observational follow-up period	Exit supervision
		Into the group	Follow-up 1	Follow-up 2	Follow-up 3	

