4.2 Grouping method and blinding level

Grouping: The study was divided into an experimental group (standard antiparkinsonian therapy + SGB) and a control group (standard antiparkinsonian therapy).

Random: Use a stratified randomization method. Group study subjects by age. After grouping, there will be 2 subgroups: ① patients aged 45-60 years, ② patients aged 61-80 years. The 2 subgroups were divided into the experimental group and the control group according to 1:1, and finally the experimental group and the control group in the 2 subgroups were pooled.

Open: Both investigators and patients were aware of the grouping of patients.

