8.1 Screening Phase (Vs, -1 Day)

During the screening visit, the following procedures will be performed/collected:

Informed consent: After introducing the study to the subjects in detail and answering the subjects' doubts, the informed consent form signed by the patients was obtained. Sign up for pre-informed laboratory tests and imaging evaluations for routine clinical care, if relevant data are available within the specified window period. (If the subjects or their guardians cannot sign the informed consent form before the trial in the event of an emergency in the project, it needs to be clearly explained here) After the informed consent, the following procedures can be carried out.

Demographics: gender, date of birth, race, education, marriage, occupational information;

Relevant medication/surgery history;

vital signs: blood pressure, pulse rate, respiration and temperature;

Physical Exam: Internal Medicine and Neurology Physical Exam;

Laboratory tests: blood routine, serum biochemistry, coagulation, ceruloplasmin, gene expression level;

Previous/concomitant medications;

Blood biomarkers: IL-2, APEO, α -synuclein, DJ-1 protein, etc.;

Imaging examination: head MRI + susceptibility-weighted imaging;

Madopa equivalent dose;

Modified MDS-UPDRS scale;

NMSS scale;

PDQ-39 scale;

H&Y;

LDE;

10M-WT;

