8.2 Randomization phase (V₁, 0 Day)

Randomize the eligible patients by stratified randomization method;

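### The between-arm primary test is fixed as an unadjusted t-test, although the screening MDS-UPDRS and the age stratum are already collected and could sharpen it at almost no cost

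*Protocol*

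**What the plan says.** Section 13.2.6 fixes the analysis of the modified MDS-UPDRS: "paired-samples t-test was used for intra-group comparison, two independent samples t-test was used for inter-group comparison", with a t' test for unequal variances. The synopsis says the same ("paired sample T test was used for intra-group comparison, two independent samples T test was used for inter-group comparison"), and section 13.2.4 repeats it. Section 13.2.2 allows a transformation or a non-parametric method if the parametric conditions fail. No section names a covariate or a stratified analysis.

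Both candidate covariates are collected. Section 8.1 lists the "Modified MDS-UPDRS scale" at screening, and the visit schedule marks MDS-UPDRS at Vs but not at V1. On allocation, section 4.2 says: "Use a stratified randomization method. Group study subjects by age". It uses two strata, 45-60 and 61-80 years, allocated 1:1 within each and then pooled. Section 8.2 confirms the stratified allocation. Section 13.2.5 plans only a description of baseline data.

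**The concern.** A pre-treatment score can enter the paired tests, but these compare each arm with itself. The baseline description adjusts nothing. So the SGB-control difference is estimated without the two pieces of pre-randomisation information that the trial already holds.

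This matters most in a trial this small. With about 15 evaluable patients per arm, the arms can differ noticeably in baseline severity by chance. The protocol also does not say whether the t-test is on the follow-up score or on the change from baseline. A chance imbalance moves those two results in opposite directions, so they can disagree. With baseline as a covariate, the treatment estimate is the same for either outcome.

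A lesser point is that the paired tests in 13.2.6 share the P < 0.05 threshold with the between-arm test although they do not compare SGB with control. The protocol does not define success by them.

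**Working it through.** **Inputs from the protocol.** Section 4.3 gives two-sided alpha 0.05, power 0.80, SD 9.58, difference 10 and loss to follow-up 20%. It does not say clearly whether 9.58 is the SD of a score or of a change, so both readings are shown. **Assumed:** the correlation r between baseline and follow-up, which the documents do not give.

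**1. The protocol's own figure.** n = (1.96 + 0.84)² × 2 × 9.58² / 10² = 14.39, so 15 per arm. Then 15 / 0.8 = 18.75, so 19 per arm and 38 in total, as stated. Conversely, 19 × 0.8 = 15.2, or about 15 evaluable per arm.

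**2. The planned t-test (noncentral t).** With 15 per arm, the standard error is 9.58 × √(2/15) = 3.50. Power is 78.8%. The 95% CI half-width is 7.17 at SD 9.58 and averages 7.10 over samples. With 19 per arm, power is 87.9%.

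**3. ANCOVA on arm, baseline and age stratum.** Its residual SD is:
- 9.58 × √(1 − r²) if 9.58 is the SD of the score;
- 9.58 × √((1 + r)/2) if 9.58 is the SD of change.

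At r = 0.5 both give 8.30. Power was simulated with a random baseline, a non-prognostic stratum split equally between arms (8 + 7 per arm) and 26 residual degrees of freedom, using 100,000 runs per cell.

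| r | Power (mean half-width), 9.58 = SD of score | Power (mean half-width), 9.58 = SD of change |
|---|---|---|
| 0.3 | 81.0% (6.93) | 91.6% (5.85) |
| 0.5 | 87.7% (6.29) | 87.6% (6.29) |
| 0.7 | 96.4% (5.18) | 83.2% (6.70) |
| 0.8 | 99.4% (4.35) | 81.2% (6.89) |

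The comparator throughout is 78.8% (7.10).

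**4. Where there is no gain.** On the score reading, power is 76.8% at r = 0, 77.5% at r = 0.1 and 78.7% at r = 0.2. On the change reading it is 79.0% at r = 0.9 and 77.9% at r = 0.95. The worst case is therefore 78.8 − 76.8 = 2.0 points lost.

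**5. All 19 per arm evaluable.** Against 87.9%, ANCOVA at r = 0.3, 0.5, 0.7 and 0.8 has 89.8%, 94.4%, 99.0% and 99.9% (score), or 96.8%, 94.4%, 91.6% and 89.9% (change). The worst case is 86.9%, 1 point lost.

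**6. Type I error.** At r = 0.5 the ANCOVA gives 5.1% (n = 15) and 5.0% (n = 19). Leaving the stratum out makes the t-test slightly conservative: 5.1%, 4.7% and 4.3% for assumed age-group gaps of 0, 3 and 5 points. Adjusting for the stratum alone changes power from 78.8%, 79.1% and 79.5% to 78.7%, 79.7% and 81.5%, a gain of at most 2 points.

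**7. Chance imbalance.** If the baseline SD is 9.58 (assumed), the difference in baseline means has SD 3.50, and P(|difference| > 5) = 15%. On the change reading the baseline SD is 9.58/√(2(1 − r)): 8.1 at r = 0.3 and 15.1 at r = 0.8, giving 9% and 37%. A 5-point imbalance shifts the unadjusted score difference by 5r, which is 1.5 to 4.0 points for r = 0.3 to 0.8. It shifts the change difference by 5(1 − r) in the opposite direction, which is 3.5 to 1.0 points. The planned difference is 10.

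**The case against.** The strongest reply is that nothing here is wrong. The t-test is valid under randomisation, it is the test that the sample size was computed for, and at 79% it essentially meets its 80% target. That stands, and it is why this is a recommendation and not an error.

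The gain depends on an r that the protocol does not give. At r = 0.3 on the score reading, or r = 0.8 on the change reading, it is only about 2 points. The highest figures need both a strong correlation and a test on the raw score. That also stands, and the range must be read as a whole.

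Chance imbalance is not bias, because the t-test's standard error already allows for it. This is correct: the shifts in step 7 show how the loss of precision arises and are not a second harm.

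The 2-point ceiling on cost assumes strata balanced between arms. If they fall at random, the loss at r = 0 is about 3.5 points and break-even moves to about r = 0.3. Allocation of 1:1 within strata largely prevents this, but section 4.2 names no block method, so the ceiling is approximate.

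Finally, covariates are often left to an analysis plan. Here, however, the protocol itself names the test, in three places, so a later plan would have to depart from it. The protocol also leaves open which MDS-UPDRS part and time point is primary. That is a larger question, but it does not remove this one.

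**Conclusion.** The point holds as an avoidable loss of precision. At 15 evaluable per arm, adjustment raises power from 79% to about 88% at r = 0.5 on either reading of the SD. Over r = 0.3 to 0.8 the gain runs from about 2 to 20 points on the score reading and from about 13 down to 2 on the change reading. The downside is about 2 points, or about 3.5 with unbalanced strata. Most of the benefit comes from the baseline score; the age stratum mainly makes the analysis match the randomisation. The figures rest on the protocol's SD of 9.58 and difference of 10, on assumed values of r, and on a linear relation between baseline and follow-up. The change should be made, but the trial would not be invalid without it.

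**What to change.** In section 13.2.6, and to match in 13.2.4 and the synopsis, make the between-arm analysis an ANCOVA of the primary MDS-UPDRS outcome on arm, screening score and age stratum. Report the adjusted difference with its 95% CI.

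- Name the Vs score as the baseline. It is the pre-randomisation score scheduled for both arms, whereas section 10.1 also mentions a cycle Day0 score.
- Replace the t' provision with a counterpart, such as a heteroscedasticity-consistent standard error. Keep the transformation and non-parametric route of 13.2.2.
- Use the same form for the continuous secondary outcomes.
- Report within-arm changes descriptively.
- Reconcile the primary MDS-UPDRS part and time point separately. For a single time point the model applies as written. If a repeated-measures outcome is chosen, baseline and stratum enter that model as covariates.

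The cost is wording and two degrees of freedom, with no new data, visits or patients. The change should be fixed before outcome data are examined, because adjustment added later in an open-label trial would look selective.
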